### Annex III. Oxford Hip Score for functional capacity and hip pain.

#### OXFORD HIP SCORE QUESTIONNAIRE

Please answer the following 12 questions. Choose only one answer per question. The value for each answer is indicated to the right of the answer. Total up all of your answers to obtain a total score out of 48 points. Please only consider how you have been getting on during the past four weeks

Name:	
Date:	
Left or right Hip?	

1. How would you describe the pain you usually have in your hip?	Score	7. Have you been able to put on a pair of socks, stockings or tights?	Score

None – 4 Very mild – 3 Mild – 2 Mild moderate – 1 Severe – 0
		
Yes, easily – 4 With little difficulty – 3 With moderate difficulty – 2 With extreme difficulty – 1 No, impossible – 0
	
2. Have you been troubled by pain from your hip in bed at night?		8. After a meal (sat at a table), how painful has it been for you to stand up from a chair because of your hip?	

No nights – 4 Only 1 or 2 nights – 3 Some nights – 2 Most nights – 1 Every night – 0
		
Not at all painful – 4 Slightly painful – 3 Moderately painful – 2 Very painful – 1 Unbearable – 0
	
3. Have you had any sudden, severe pain-'shooting', 'stabbing', or 'spasms' from your affected hip?		9. Have you had any trouble getting in and out of a car or using public transportation because of your hip?	

Rarely/never – 4 Sometimes or just at first – 3 Often, not just at first – 2 Most of the time – 1 All of the time – 0
		
No trouble at all – 4 Very little trouble – 3 Moderate trouble – 2 Extreme difficulty – 1 Impossible to do – 0
	
4. Have you been limping when walking because of your hip?		10. Have you had any trouble with washing and drying yourself (all over) because of your hip?	

Rarely/never – 4 Sometimes or just at first – 3 Often, not just at first – 2 Most of the time – 1 All of the time – 0
		
No trouble at all – 4 Very little trouble – 3 Moderate trouble – 2 Extreme difficulty – 1 Impossible to do – 0
	
5. For how long have you been able to walk before the pain in your hip becomes severe (with or without a walking aid)?		11. Could you do the household shopping on your own?	

No pain for 30 minutes or more – 4 16 to 30 minutes – 3 5 to 15 minutes – 2 Around the house only – 1 Not at all – 0
		
Yes, easily – 4 With little difficulty – 3 With moderate difficulty – 2 With extreme difficulty – 1 No, impossible – 0
	
6. Have you been able to climb a flight of stairs?		12. How much has pain from your hip interfered with your usual work, including housework?	

Yes, easily – 4 With little difficulty – 3 With moderate difficulty – 2 With extreme difficulty – 1 No, impossible – 0
		
Not at all – 4 A little bit – 3 Moderately – 2 Greatly – 1 Totally – 0
	

**Total Score:** /48

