**Table II (continuation): Patient follow-up variables**

Variables	Unit of measurement	Type
Functional Capacity and Pain (Oxford Hip Score)	Points (0 to 48)	Quantitative and Qualitative
Falls Risk (STRATIFY Scale)	Points (0 to 5)	Quantitative and Qualitative
Medical complications	0= Fall. 1= Pneumonia. 2= New fractures. 3= Dementia. 4= Acute Myocardial Infarction 5= Pulmonary embolism. 6=Deep vein thrombosis; 7=Death.	Qualitative
Quality of life analysis: questionnaire EQ-5D-5L	Levels (1 to 3125) Points (0 to 100)	Qualitative Quantitative
Abbreviations: RNFC: National Hip Fracture Registry, mFAC: Modified Functional Ambulatory Classificator,		

- **Level of dependency: the Spanish version of the *Barthel Index* will be used (Annex I).** The "*Barthel Index*" provides quantitative information on the level of dependence for activities of daily living by measuring ten activities that are considered basic (441,42). This scale has been used in other studies and shows a direct relationship between high levels of dependency and poor physical health (441). "The Barthel Index has demonstrated good inter-observer reliability, with Kappa indices between 0.47 and 1.00, intra-observer reliability with a Kappa index between 0.84 and 0.97 and internal consistency with a Cronbach's alpha of 0.86-0.92 (39-41).

Test results:

- Values: 0-20 total dependency.
- Values: 21-60 severe dependence.

- Values: 61-90 moderate dependence.
- Values: 91-99 low dependency
- Values: 100 independence.

This scale is administered at 6 weeks, 4 months and 1 year.

- **Sarcopenia assessment: using the SARC-F scale (ANNEX II) (42).**

It is an easily accessible questionnaire, validated in Spanish, which allows the identification of subjects at risk of sarcopenia. The maximum score is 10 points. A score of < 4 points after the test indicates an acceptable state of health, while any score higher than this indicates a risk of sarcopenia (43).

This scale is administered at 6 weeks, 4 months and 1 year.

- **Assessment of functional capacity and specific hip pain: "Oxford Hip Score (OHS)" (ANNEX III)**

It has high repeatability and reliability, with a Cronbach's Alpha value of 0.84 preoperatively, ICC=0.94, and 0.89 at six months and one year (44).

It is a 12-item questionnaire, each item is answered on a five-level Likert-type scale where 4 is the minimum impact and 0 the most unfavourable (45).

Results:

0-19: Severe impact.

20-29: Moderate to severe impact.

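### Oxford Hip Score form (Annex III): item 3 carries the limping answers of item 4, and item 1 has no distinct moderate grade, so up to 8 of 48 points rest on unclear answers if the app uses this wording

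*Combined protocol and SAP*

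**What the plan says.** The follow-up variables section (Table II, continuation, and the text below it) describes the score thus: "It is a 12-item questionnaire, each item is answered on a five-level Likert-type scale where 4 is the minimum impact and 0 the most unfavourable". It supports the score with published reliability figures (alpha 0.84 before surgery, ICC 0.94, and 0.89 at six months and one year). It sorts the total into four impact classes: 0-19, 20-29, 30-39 and 40-48. Table III schedules the score at 1, 3, 6 and 12 months.

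Annex III is the form itself, with the instruction "Total up all of your answers to obtain a total score out of 48 points". Two items matter here:

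- Item 1 asks "How would you describe the pain you usually have in your hip" and offers "None – 4 Very mild – 3 Mild – 2 Mild moderate – 1 Severe – 0".
- Item 3 asks "Have you had any sudden, severe pain-'shooting', 'stabbing', or 'spasms' from your affected hip". Its middle answers are "Sometimes or just at first – 3 Often, not just at first – 2". Item 4, on limping when walking, prints the same five answers.

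The introduction to the second group of variables says that these variables can be measured only in the 2021 (unexposed) cohort. Describing patient-reported outcomes in that cohort is one of the specific objectives.

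**The concern.** An answer set has to fit its question. For limping, a phrase about the start of the activity makes sense: the limp may fade after the first steps. Sudden shooting pain has no such start, so two of the five answers to item 3 have no clear meaning. In item 1 a patient with moderate pain finds no grade with that plain name, only a label joining mild and moderate, placed directly above *Severe*.

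The score is the study's only hip-specific measure of pain and function. Published reliability belongs to the wording on which it was measured, and the impact classes are cut from the total. Neighbouring annexes suggest that the printed forms were not proofread. In Annex II the question on the number of falls has the same answers as the stairs question, including being unable. The EQ-5D-5L is described with five levels per dimension, but Annex IV prints three.

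**Working it through.** **1. The plan's own figure.** 12 items × 4 points = 48. This matches the stated maximum.

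**2. Item 3 against item 4.** The five answers, codes 4 to 0, are identical. Codes 4, 1 and 0 are plain frequencies and suit either question. The phrases that suit only an activity with a beginning sit on codes 3 and 2.

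**3. Item 1 against the rest of the form.** Items 6 to 12 all use moderate as a plain grade, at code 2: moderate difficulty (6, 7, 11), moderately painful (8), moderate trouble (9, 10), moderately (12). Item 1 has *Mild* at code 2 and *Mild moderate* at code 1. This shows an inconsistent label. It does not show that code 1 is the wrong value for moderate pain, because item 1 gives two of its grades to mild pain.

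**4. Share of the score.** Items 1 and 3 together: 2 × 4 = 8 points; 8/48 = 16.7%. This is an upper bound, since it counts every answer of both items as unclear.

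**5. Size of a shift.** In item 1 a patient with moderate pain hesitates between codes 1 and 0, a difference of 1 point. For item 3 the documents give no basis for a size.

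**6. Effect on the impact classes.** The cut points are 19/20, 29/30 and 39/40.

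- A downward shift of 1 point is possible from totals 1 to 48 (48 totals). It changes the class from 20, 30 and 40: 3/48 = 6.3%.
- A downward shift of 2 points (assumed: both items off by one, in the same direction) is possible from totals 2 to 48 (47 totals). It changes the class from 20, 21, 30, 31, 40 and 41: 6/47 = 12.8%.

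These are shares of possible totals, not of patients. The documents do not give the distribution of totals or the number of patients with moderate pain.

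**The case against.** The strongest reply is that the printed page may not be what patients see. Under Data collection procedure, answers are entered in an app by patients in León or their caregivers, while Annex III is in English. The document has translation faults elsewhere (Table I codes the right side as *Law*; Table III speaks of *March Capacity*). A garbled label may therefore be a fault of the annex only. This stands: harm to the data is conditional, and a check must come first.

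It can also be said that the answers remain usable. All items keep five ordered codes. Item 3 still reads as a frequency scale, and if *Mild moderate* is a misprint for moderate at the same code, item 1 shifts nothing. This stands in part. It makes a large shift unlikely, but it does not make the answers to item 3 fit their question.

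Three stronger readings are tempting and are not supported:

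- **That a quarter of the score is affected.** A reader might add item 5, where "No pain for 30 minutes or more – 4 16 to 30 minutes – 3" lets 30 minutes fit two answers; 12/48 = 25%. Of the whole minutes from 0 to 60, only exactly 30 fits two timed answers. These have adjacent codes 1 point apart, and nothing in the documents shows that item 5 departs from the validated wording.
- **That patients answer alone with nobody to help.** A caregiver may enter the data, the limitations section plans team support for those in difficulty, and the work plan provides a contact for doubts. None of these is described as correcting an ill-fitting answer, but patients are not unsupported.
- **That the printed form is known to depart from the validated one.** The validated form is not in the documents. That the answers to item 3 were copied from item 4 is an inference from identical text.

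**Conclusion.** The point holds for items 1 and 3. If the app uses the wording of Annex III, up to 8 of 48 points (16.7%) rest on unclear answers, and the quoted reliability cannot be assumed to carry over. The likely effect of item 1 on the total is small, at most 1 point for a patient with moderate pain. The effect of item 3 cannot be sized from the documents. A shift of 1 or 2 points moves the impact class only from totals close to a cut point.

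A reader might infer that the comparison of the programme with earlier care is biased. It is not: the score is collected only in the 2021 cohort, and the overall objective is return to function before the fracture. The consequence is limited to the description of patient-reported results in that cohort. The verdict rests on one assumption that the documents cannot settle, namely that the app shows the printed wording.

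**What to change.** 1. Name the version of the score in use and compare both Annex III and the app text with the validated Spanish version, item by item. Correct items 1 and 3 where they differ. Leave item 5 as it is unless this check shows a discrepancy.
2. If the app already carries the validated wording, correct the annex only; no analysis changes.
3. If responses were collected on the printed wording, say so in the report and add a sensitivity analysis with two reduced totals. Without item 3 the maximum is 48 − 4 = 44, so multiply by 48/44 = 1.091. Without items 1 and 3 it is 48 − 8 = 40, so multiply by 48/40 = 1.2. Rescale before applying the impact classes, which assume a maximum of 48. Rescaled totals are not always whole numbers, so state beforehand how values between 19 and 20, 29 and 30, and 39 and 40 are classed.

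The cost is one comparison of texts, a small correction to the form and perhaps to the app, and one extra table if data already exist.

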**Annex IV. Questionnaire EQ-5D-5L for quality of life**

**Mobility**

I have no problems in walking about

I have some problems in walking about

I am confined to bed

**Self-Care**

I have no problems with self-care

I have some problems washing or dressing myself

I am unable to wash or dress myself

**Usual Activities (e.g. work, study, housework, family or leisure activities)**

I have no problems with performing my usual activities

I have some problems with performing my usual activities

I am unable to perform my usual activities

**Pain/Discomfort**

I have no pain or discomfort

I have moderate pain or discomfort

I have extreme pain or discomfort

**Anxiety/Depression**

I am not anxious or depressed

I am moderately anxious or depressed

[figure not shown]
I am extremely anxious or depressed

#### Annex IV. EQ-5D-5L Quality of Life Questionnaire (continued)

To help people say how good or bad a health state is, we have drawn a scale (rather like a thermometer) on which the best state you can imagine is marked 100 and the worst state you can imagine is marked 0.

We would like you to indicate on this scale how good or bad your own health is today, in your opinion. Please do this by drawing a line from the box below to whichever point on the scale indicates how good or bad your health state is today.

**Your own  
health state**

## Annex V: Work Plan

## Annex VIII: Functional recovery programme.

### **LEVEL 1: EXERCISES FOR BED PATIENTS**

#### **Ankle flexion-extension movement.**

Slowly push your foot up and down. Repeat this exercise several times, up to every 5 to 10 minutes.  
Begin this exercise immediately after surgery and continue until you fully recover.

#### **Ankle rotations**

Move your ankle inward, toward the other foot, and then outward, away from the other foot.  
Repeat 5 times in each direction.  
Do this exercise 3 or 4 sessions a day.

#### **Bed-supported knee curls**

Slide your foot toward your buttocks, bending your knee and keeping your heel on the bed. Don't let your knee roll inward. Hold your knee in the maximum flexed position for 5 to 10 seconds and then stretch it out.  
Repeat 10 times.  
Do 3 or 4 sessions a day.

#### **Gluteal contractions**

Tighten your glute muscles and keep them for a count of 5.  
Repeat 10 times.  
Do 3 or 4 sessions a day.

#### **Open legs exercise**

Slide your leg to the side as far as possible and then back.  
Repeat 10 times.  
Do 3 or 4 sessions a day

#### **Thigh strengthening**

Tighten the thigh muscle. Try straightening your knee. Hold for 5 to 10 seconds.  
Repeat this exercise 10 times over a 10 minute period, rest for one minute, and repeat.  
Continue until your thigh feels fatigued.

#### **Straight leg raises**

Squeeze your thigh muscle with your knee fully stretched out on the bed. Raise your leg several inches. Hold for 5 to 10 seconds. Lower slowly.  
Repeat until your thigh feels fatigued.

## **LEVEL 2: EXERCISES TO BE PERFORMED STANDING**

Shortly after surgery, you will be out of bed and able to stand. You will need help at first, but as you regain strength you will be able to support yourself independently. As you do these exercises while standing, be sure to hold on to a firm surface, such as a bar attached to your bed or a wall.

### **Seated knee extension exercise**

With your leg bent and your foot flat on the floor, straighten your knee and then flex your foot, bringing your toes toward you. Hold for 5 seconds and then lower your leg.  
Repeat 10 times.  
Do 3 or 4 sessions a day.

### **Standing knee raise**

Raise your operated leg toward your chest. Do not lift the knee above the waist. Hold for 2-3 seconds and lower your leg.  
Repeat 10 times.  
Do 3 or 4 sessions a day.

### **Leg separation movements**

Make sure ~~your~~ hip, knee, and foot point forward. Keep your body straight. With your knee straight, bring your leg to the side. Slowly lower your leg so that your foot returns to the ground.  
Repeat 10 times.  
Do 3 or 4 sessions a day.

### **Standing hip extensions**

Slowly lift your operated leg back. Try to keep your back straight. Hold for 2 or 3 counts. Return your foot to the floor.  
Repeat 10 times.  
Do 3 or 4 sessions a day.

### **Sit-up exercise from a chair**

Straighten the operated leg without bending the knee and lean on the armrest of the chair. Lean forward slightly and supporting your weight on your good leg and your hands slowly rise  
Repeat several times.  
Do 3 or 4 sessions a day.

### **LEVEL 3: INTERMEDIATE EXERCISES GROUP**

Los pacientes realizarán 5 ejercicios sentados o acostados ~~más~~ una pequeña cantidad de caminata utilizando ayudas para caminar durante un total de 30 minutos. Los ejercicios deben ser realizados de forma progresiva aumentando las repeticiones y la resistencia.

Patients will perform 5 exercises sitting or lying down plus a small amount of walking using walking aids for a total of 30 minutes. The exercises should be done progressively, increasing repetitions and resistance.

#### **To walk**

Walking properly is the best way to help your hips heal. At first, you will walk with a walker or crutches. Your surgeon will tell you how much weight you can put on your leg. Walking will help you regain movement in your hips.

Stand comfortably and upright with your weight balanced evenly on your walker or crutches. Advance your walker or crutches a slight distance first; Slowly stretch the operated leg forward with your knee fully extended until the heel of the foot touches the ground. As your body moves forward, your entire foot will make contact with the ground. Then move your good leg up to the level of the foot of the operated leg.

Walk comfortably and smoothly. Do not rush. Adjust your stride length and speed so that it is comfortable for you and you can make a smooth pattern. As your muscle strength and endurance improve, you may spend more time walking. As time goes by, you will put more weight on your leg and then you can use a cane in the hand opposite the operated leg and eventually walk without assistance.

When you can walk and stand for more than 10 minutes and your leg is strong enough not to put weight on your walker or crutches, you can start using a single crutch or cane. Hold the aid in the hand opposite the side of your surgery.

[figure not shown]
#### **Walking with a walker**

First, forward the walker, then advance with the operated leg without bearing much weight, finally, advance the good leg.

#### **Walking with crutches**

First, forward both crutches, then advance with the operated leg without bearing much weight, finally, advance the good leg.

#### **LEVEL 4: GROUP OF INTERMEDIATE EXERCISES TO GO UP AND DOWN STAIRS**

##### **Up and down stairs**

The ability to go up and down stairs requires strength and flexibility. At first, you will need a handrail for support and will only be able to go one step at a time. Always go up the stairs with your good leg and go down the stairs with your operated leg. You may want someone to help you until you have regained most of your strength and mobility. Climbing stairs is a great strength and endurance activity. Do not attempt to climb steps higher than the standard height (18 cm) and always use a handrail for balance. As you get stronger and more mobile, you can start climbing stairs step by step.

[figure not shown]
[figure not shown]
##### **Climbing stairs**

Place the good leg on the step, then raise the operated leg and finally raise the poles.

##### **To go down the stairs**

Place the poles on the bottom rung, lower the operated leg and finally lower the operated leg.

## **LEVEL 5: ADVANCED EXERCISES GROUP**

Walking and strength and balance exercises for a total of 60 minutes a day.

### **Sit / stand up**

Sit on the edge of the chair with your cushion raised. Lifts from the chair and sit back several times. First begin to do it with the operated leg in front and as you are able to flex the leg more, slow down your position. Don't bend your hips more than 90 degrees. Repeat 8 to 15 times.

### **Step up / step down**

Use handrails to keep your balance. Place one foot on a step and step forward by lifting your body. Then go back to the starting position. This exercise should be done with both legs (first one 8-15 repetitions and then the other). As you find yourself with more force, you can decrease the help of the handrail.

Repeat 8 to 15 times.

### **Shifting weight back and forth.**

Stand next to a stable support and prop one heel in front of the other foot. Shift your weight back and forth through the balls of your feet, staying upright.

Repeat 20 to 30 times.

As you feel stronger and more confident, gradually remove the support from the support.

### **Standing knee raise**

Raise your operated leg toward your chest. Do not lift the knee above the waist. Hold for 2-3 seconds and lower your leg.

Repeat 10 times.

Do 3 or 4 sessions a day.

### **Leg separation movements**

Make sure your hip, knee, and foot point forward. Keep your body straight. With your knee straight, bring your leg to the side. Slowly lower your leg so that your foot returns to the ground.

Repeat 10 times.

Do 3 or 4 sessions a day.

[figure not shown]

### **Transfer exercises**

#### **Get out of bed**

If you stand on the side of your good leg: Leave your operated leg straight, being careful not to twist it. Support yourself with your elbow and forearm on the good side and move closer to the edge of the bed. Get your good leg out of bed and push yourself up with the help of your elbow and forearm. Once sitting on the edge of the bed, you can stand up, as long as you are not dizzy.

If you stand up on the side of the operated leg: Bend your good leg over the bed, leave your operated leg straight with the toe facing up. Get on your elbows and take the operated leg out of the bed, get up with the help of your arms until you get to the sitting position.

#### **Get out of bed**

You must do the reverse process: bend your good leg supporting the operated leg on the bed. Once the good leg is supported, be careful not to twist it, the foot must always face upwards. Drop onto the bed leaning on your elbow and forearm.

#### **Go to the bathroom.**

You must go through the same process as getting up from a chair. Remember that there are some adapters that can facilitate the process

## **RECOMMENDATIONS**

### **Do not cross your legs**

You should not sit in low chairs for a long time, or stay cross-legged.

### **Do not rotate the hips when loaded**

The hips should not remain rotated. Remember that your toes and knee should point forward.

### **How should you sleep**

During the early stages, you should not lie flat on either of your hips for a long time. The best way is to sleep on your back and with a pillow separating the two legs.
